We previously studied the reliability of a commercially available Dexcom G6 CGM (Dexcom, Inc., San Diego, CA) under hyperbaric oxygen conditions in healthy volunteers who did not have diabetes. This showed an increase of 3.76 mg/dL (3.72%, p<0.001) while patients were breathing HBO₂ at 2.4 atmospheres absolute (ATA) and an increase of 4.12 mg/dL (4.13%, p=0.015) when comparing pre-HBO₂ and post-HBO₂ values. The increase in EGV may have been related to increases in interstitial fluid temperature related to the HBO₂, but that was not measured. While this was statistically significant, it was not felt to be clinically relevant. The Dexcom G6 CGM was felt to be accurate and reliable for use with patients without DM receiving HBO₂. The goal for this proposed study is to look at multiple CGMs in patients with DM receiving HBO₂.

Research Goals

Specific Aim 1 – Determine whether the Dexcom G6 CGM accurately estimates blood glucose under hyperbaric oxygen conditions

Specific Aim 2 – Determine whether a single HBO₂ treatment affects blood glucose in patients with diabetes mellitus

Specific Aim 3 – Determine whether glucagon varies in relationship with HBO₂

Materials and Methods

Study Design and Timeline

This will be a prospective, controlled trial comparing a standard HBO₂ treatment vs. a control period. Each patient will serve as their own control.

December 4, 2019

Recruitment

We will recruit individuals who are living with type 1 or type 2 diabetes and are willing to undergo a single hyperbaric exposure to 2.4 ATA while breathing 100% oxygen. Participants will provide their informed consent after the risks of the study have been explained to them (*e.g.*, HBO₂ possibly decreasing BG) and the risks of HBO₂ (*e.g.*, barotrauma, confinement anxiety, oxygen toxicity, and fire). Upon enrollment in to the study, participants will have a commercial G6 CGM inserted in the subcutaneous tissue of their abdomen and a research G6 data logger inserted in the subcutaneous tissue on the back of the arm. Participants will return >36 hours after insertion for their study exposures.

Compensation up to \$400 will be pro-rated to encourage completion of all study sessions (Figure 1):

- Implantation of CGM loggers - \$50
- Completion of control study session - \$50
- Completion of HBO₂ study sessions- \$100
- Completion of follow-up data collection - \$200

Figure 1. Study Timeline and Compensation Schedule

Day		Day 1	36 hour interval	Day 3	Day 4	Day 5-9	Day 10

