- Patients with meal-time doses of insulin should hold their meal-time boluses until they eat their first meal of the day
- Patients who require a correction dose of insulin the morning of study session (control of HBO₂) because of a blood glucose >250 mg/dL should take their normal dose of insulin and document it in their medication log
- Patients who use long-acting insulin should modify their doses as follows
 - Patients who are on BID long-acting insulin to take their normal dose in the morning, but 2/3 of their dose the night before
 - Patients who are on night-time long-acting insulin to take 2/3 their normal dose the night before
 - Patients who are on morning long-acting insulin to take 2/3 of their normal dose in the morning

Study investigators will review insulin doses and provide additional instructions for adjustment if needed for safety.

Modification of the Hyperbaric Department Glucose Protocol

The hyperbaric department currently follows a protocol to provide supplemental carbohydrates to patients with a pre-HBO₂ BG <100 mg/dL whether they are

December 4, 2019

symptomatic or not. We will be following the hyperbaric department protocol and obtaining pre-HBO₂ fingerstick blood sugars, but we will not provide mandatory supplemental carbohydrate for BG <100 mg/dL unless participants complain of symptoms they associate with hypoglycemia. If participants are documented to have hypoglycemia – defined by the American Diabetes Association (ADA) as a BG ≤ 70 mg/dL¹⁰ – before or during study periods, we will institute the hyperbaric department’s hypoglycemia protocol and provide 15 grams of supplemental carbohydrate. Hypoglycemia risk to the patient is mitigated because we will be able to monitor blood sugar in real time using CGM, however clinical decisions will be made using the fingerstick GDH-based POC glucometer.

Transcutaneous Oxygen Monitoring during HBO₂ exposures

We will obtain concurrent transcutaneous oximetry measurements (TCOM) using a Clarke electrode (Radiometer America, Brea, CA) attached no farther than 3 cm from the commercial CGM on the abdomen to measure tissue oxygenation in the region of the CGM only during HBO₂ exposure. The TCOM value closest to the time of each blood draw will be used for analysis. The average pre-HBO₂ TCOM measurements will be used as a surrogate for the control day TCOM.

Hemoglobin A1c

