We will obtain a single Hba1c measurement using the central laboratory chemistry analyzer (AU680 Chemical Chemistry Analyzer, Beckman Coulter, Inc., Brea, CA) at the first blood draw to establish baseline control of their DM.

Blood glucose (central laboratory)

We will use the central laboratory chemistry analyzer (AU680 Chemical Chemistry Analyzer, Beckman Coulter, Inc., Brea, CA) to measure blood glucose at each of the time points (Figure 4). This analyzer uses a hexokinase reaction that is insensitive to blood oxygen levels and will serve as the reference for CGM and POC glucometers.

Glucagon (send-out to OHSU)

We will draw blood glucagon before (Timepoint 1), during (Timepoint 9), and after (Timepoint 12) actual or simulated HBO₂ (Figures 2-4) in order to determine whether there are any effects of HBO₂ on glucagon. The protocol for the glucagon handling is described below.

Blood sampling schedule (Figure 4)

We will obtain a venous blood glucose sample on all participants at the following time points during the study (± 2 min):

1. 30 minutes prior to starting (NBAir)
2. 15 minutes prior to starting (NBAir)
3. Immediately prior to study session (NBAir)

10-minute compression

4. 15 minutes into O₂ period 1 (HBO₂)
5. 30 minutes into O₂ period 1 (HBO₂)
6. 15 minutes into O₂ period 2 (HBO₂)
7. 30 minutes into O₂ period 2 (HBO₂)
8. 15 minutes into O₂ period 3 (HBO₂)
9. 30 minutes into O₂ period 3 (HBO₂)

5-minute decompression

10. Immediately after reaching 1 ATA (NBAir Post-HBO₂)
11. 15 minutes after reaching 1 ATA (NBAir Post-HBO₂)
12. 30 minutes after reaching 1 ATA (NBAir Post-HBO₂)

Figure 4. Timeline of testing

	Pre-HBO ₂			HBO ₂						Post-HBO ₂		
Control/HBO ₂	1	2	3	4	5	6	7	8	9	10	11	12
Time \pm 2min	T-30	T-15	T0	T+25	T+40	T+60	T+75	T+95	T+110	T+115	T+130	T+145
CGM EGV	•	•	•	•	•	•	•	•	•	•	•	•
CGL EGV	•	•	•	•	•	•	•	•	•	•	•	•
Interstitial T ⁺	•	•	•	•	•	•	•	•	•	•	•	•
Lab Glucose	•	•	•	•	•	•	•	•	•	•	•	•
NovaStat	•	•	•	•	•	•	•	•	•	•	•	•
AccuChek	•	•	•	•	•	•	•	•	•	•	•	•
TCOM	•	•	•	•	•	•	•	•	•	•	•	•
Glucagon	•							•				•

December 4, 2019

Because we are using a saline-locked peripheral IV with a 4-way stopcock for blood sampling, our protocol for each blood draw will be as follows:

- Draw approximately 4 ml of venous blood from distal port of the IV catheter, leaving the syringe in place;
- Withdraw 2 ml of venous blood and place in purple top for measurement of glucagon;

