- Return the 4 ml of venous blood through proximal port and flush with 10-20 ml of normal saline until line is clear of blood;
- Cap the port with a clean 1 ml syringe;

For glucagon processing

- Prechill a lavender top (EDTA) with aprotinin tube at 4°C before drawing the specimen
- Draw the prechilled lavender (EDTA) top tube and process 2.0 mL of EDTA plasma as follows:
 - Sample should be mixed by inverting gently 6-7 times;
 - Chill lavender (EDTA) top tube in wet ice for 10 minutes;
 - Centrifuge in a refrigerated centrifuge (4 °C) or in chilled centrifuge cups;
 - Spin at ≈2600 RPM in the centrifuge with samples balanced;
 - Aliquot plasma into appropriate number cryo-tubes using a separate transfer pipette for each tube;
 - Freeze samples ASAP in freezer

A runner will process each glucagon sample immediately after removal from the hyperbaric chamber. Frozen glucagon samples will be batched and transported to the OHSU laboratory on dry ice for processing.

December 4, 2019

Fingerstick point-of-care glucose testing

Because we have not established that CGMs are reliable under HBO₂ conditions, we will collect POC glucose measurements using the hospital's standard GOx-based NovaStat POC glucometer (Nova Biomedical, Waltham, MA) and a GDH-based AccuChek Inform II POC glucometer (Roche Diagnostics, Indianapolis, IN) at each testing point. We will compare the POC glucometer readings against the laboratory readings to generate a mean absolute relative difference (MARD) for each glucometer. Because GOx-based POC glucometers are known to underestimate BG while GDH-based POC glucometers do not, we will primarily use the AccuChek GDH-based POC glucometer for clinical decision making.

Fingerstick protocol

1. Clean the subject's fingertip with soap and water and allow to dry.
2. Puncture the skin with one quick stroke with the lancet to achieve a good flow of blood.
3. Wipe away the first drop of blood as it may be contaminated with plasma or debris.
4. Blood collection - Avoid squeezing the finger too tightly as this will dilute the specimen with plasma and increase the probability of hemolysis.
 - a. At 1 ATA - gently squeeze the finger and apply blood to the test strip.
 - b. At 2.4 ATA - gently squeeze the finger and collect blood in micro-pipette.
5. When the blood collection procedure is complete, apply firm pressure to the site to stop the bleeding.

Continuous glucose monitor

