- Use of CGM devices does not present a potential for serious risk to the health, safety or welfare of a subject.

There is a very low risk of developing a local skin infection at the site of the sensor placement and a very low risk of sensor breakage. The participant will be instructed to notify study staff if they develop swelling, redness, or pain at the sensor insertion site.

Adverse Events

We will catalog adverse events associated with HBO₂ (e.g., otic/sinus barotrauma, O₂ toxicity, confinement anxiety) or severe hypoglycemia (BG < 70 mg/dL) associated with HBO₂. We will report any complications related to the insertion of the CGM or fingersticks related to home glucose testing. Asymptomatic patients with a BG <100

December 4, 2019

mg/dL will not be considered an adverse outcome associated with HBO₂ but will be counted for analysis.

Analysis

Endpoint 1

In order to determine the accuracy of the G6 CGM in patients with diabetes who are receiving HBO₂, we will compare CGM values to laboratory results in the pre-HBO₂ NBAir (1-3), HBO₂ (4-9), and post-HBO₂ NBAir (10-12) phases. We will compare the mean absolute relative difference (MARD), which is listed at 9.9% in the Dexcom G6 user guide and has a standard deviation of 7.99 mg/dL. If we are trying to detect a difference of 5 percentage points in MARD (9.9% in room air up to 14.9% in HBO₂) with a standard deviation of 8 mg/dL, alpha level ($p < 0.05$), and a power of 0.80, we will require a minimum sample size of 18 patients.

Endpoint 2

We will compare CGM and venous blood glucose readings before (1-3), and after (10-12) each study session and use this to determine if there is any effect of session type (HBO₂ vs control) on BG. Each individual will serve as their own control, which will improve the study's power. We will determine if the BG changes observed during HBO₂ sessions are greater than those observed when the participants are sitting quietly outside the chamber during the control sessions. Linear mixed effects regression (LMER) analyses will be used to account for the clustering of data within an individual while also allowing for the main effect (difference in pre- vs. post- by session type) to be determined.

Endpoint 3

We will evaluate whether a single HBO₂ treatment affects glucagon levels by comparing control glucagon levels with the pre-, intra-, and post-HBO₂ glucagon levels.

December 4, 2019

Estimated time to conduct study

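### Endpoint 1 judges CGM accuracy by unsigned MARD alone, so a directional sensor error under HBO₂ could go largely unseen; it also leaves open whether the control day is used

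*Combined protocol and SAP*

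**What the plan says.** Under Analysis, Endpoint 1, "we will compare CGM values to laboratory results in the pre-HBO₂ NBAir (1-3), HBO₂ (4-9), and post-HBO₂ NBAir (10-12) phases". The measure is then named: "We will compare the mean absolute relative difference (MARD), which is listed at 9.9% in the Dexcom G6 user guide". The sample size rests on a rise in MARD from 9.9% to 14.9%. No signed error, mean bias or limits of agreement is named for the CGM anywhere in the document.

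The reference method suits a signed analysis. Of the central laboratory analyser the plan says: "This analyzer uses a hexokinase reaction that is insensitive to blood oxygen levels and will serve as the reference for CGM and POC glucometers".

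The control session carries the same sampling. Figure 1 lists 12 venous laboratory glucose samples on the control day, the Control Protocol section runs the draws in parallel with the HBO₂ day, the timeline of testing has a joint control and HBO₂ row, and the budget covers 24 laboratory glucose tests per subject. Endpoint 1 does not mention this session. Endpoint 2 does use both sessions: "We will compare CGM and venous blood glucose readings before (1-3), and after (10-12) each study session". Its aim is the effect of session type on blood glucose, and it leaves out readings 4-9.

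**The concern.** Specific Aim 1 asks whether the G6 estimates glucose accurately under hyperbaric oxygen. An oxygen effect on the sensor would probably have a direction. A uniform shift pushes some errors away from zero and others towards it, so the average absolute error moves little, and it falls if the sensors read low to begin with. A fall in MARD would correctly report better average accuracy while hiding that oxygen had moved the readings.

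The Background reports that G6 readings in volunteers without diabetes rose 3.72% during HBO₂ and 4.13% from before to after it. No laboratory reference is stated for those rises, so glucose or the sensor may have moved. This trial has the reference needed to separate the two in patients with diabetes, but the named metric discards the sign that would do it.

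The second issue is distinct. Without a stated session contrast at readings 4-9, a change in CGM error within the HBO₂ day cannot be separated from the effects of time, fasting or sensor lag.

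**Working it through.** **1. The plan's own figure.** Inputs from Endpoint 1: difference 5 points, SD 8 (printed in mg/dL, taken here as percentage points), alpha 0.05, power 0.80. A one-sample or paired t-test with one-sided alpha needs n = 17.3, so 18, which matches the plan (power 81.6%). With two-sided alpha it needs 23; power is 70.5% at 18 and 83.4% at the planned 24. Everything below is two-sided at n = 24.

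**2. What a shift does to MARD.** Assume relative error is normal with mean b and SD σ. Then MARD = σ√(2/π)·exp(-b²/2σ²) + b·[1 - 2Φ(-b/σ)]. Setting MARD to 9.9 gives σ = 9.9/√(2/π) = 12.41 at b = 0, and σ = 11.73 at b = ±4. Replacing b by b + shift:

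| Baseline bias b | Change in MARD, shift +3.72% | Shift needed to reach 14.9% |
|---|---|---|
| -4% | -0.54 | about +17% |
| 0 | +0.44 | about +13% |
| +4% | +1.42 | about +9% |

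The result depends on baseline bias. For a +10% shift at b = +4 the mean error is 14, and MARD = 9.36 × 0.491 + 14 × 0.767 = 15.3, a rise of 5.4 points. At b = -4 the mean error is 6, and MARD = 9.36 × 0.877 + 6 × 0.391 = 10.6, a rise of only 0.7.

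**3. Power.** Assumed: total error SD 12.41%, reading noise SD 6%, phase-to-phase sensor wander w of 0, 4 or 8%, the rest a constant bias per sensor averaging zero. The shift applies only to readings 4-9 on the HBO₂ day. The signed same-day change has SD √(2w² + 36/3 + 36/6) = 4.24, 7.07 or 12.08. The session contrast multiplies this by √2. Power comes from 20,000 simulated trials per case; the MARD ranges allow for differences between repeat runs.

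| Test | +3.72%, w = 0/4/8 | +10%, w = 0/4/8 | 95% half-width, points |
|---|---|---|---|
| MARD, HBO₂ day | about 6-8% throughout | about 32-47%, lowest at w = 8 | not calculated |
| Signed, HBO₂ day | 98/69/30% | 100/100/97% | 1.8/3.0/5.1 |
| Signed, HBO₂ minus control | 83/41/17% | 100/100/79% | 2.5/4.2/7.2 |

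At w = 8 the paired MARD SD is about 8, near the plan's value; at w = 0 it is 3.6 to 4.5. If the plan's 8 describes single readings and not paired differences, w is not identified.

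**4. Sensor lag can imitate a shift.** Assume glucose of 150 mg/dL at T0 falling 0.5 mg/dL/min, and a CGM that reports the value of 15 minutes before. Once the fall is established, the CGM reads 7.5 mg/dL high. Relative to the glucose at each scheduled time, this averages 4.77% at readings 1-3, 6.56% at 4-9 and 8.87% at 10-12. With no oxygen effect, the signed change is therefore 6.56 - 4.77 = 1.8 points at 4-9 and 8.87 - 4.77 = 4.1 at 10-12, if the fall began well before T-30. If it began at T-30, reading 1 has no error, the 1-3 mean is 3.25, and the changes are 3.3 and 5.6 points. For 4-9 vs 1-3, the same-day signed test would flag 1.8 points in 51/22/11% of trials. At 3.3 points (3.3√24/SD in the noncentral t) it would flag about 95/59/25%.

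**The case against.** - **The Background shift may not matter.** The protocol says the rise was not felt to be clinically relevant, and the plan is powered for a 5-point change in MARD. This stands, although that judgement concerned people without diabetes. The stronger case is a +10% shift, which MARD would usually miss when average baseline bias is near zero.
- **A reader might infer that a 3.72% sensor error has already been shown.** It has not. The Background reports a rise in readings without a stated reference, so the figure illustrates size only.
- **A reader might infer that the missing control contrast causes the insensitivity.** It does not. Adding the contrast while keeping MARD leaves power for +3.72% at about 5-7%. The unsigned metric is the cause.
- **A reader might infer that the control day was left out of Endpoint 1.** The text does not settle this. The design statement, "This will be a prospective, controlled trial comparing a standard HBO₂ treatment vs. a control period", and the oximetry rule, "The average pre-HBO₂ TCOM measurements will be used as a surrogate for the control day TCOM", may imply that both sessions are meant.
- **Endpoint 2 gives partial cover.** It compares signed CGM and venous changes by session, so reporting them side by side would show divergence at readings 10-12. Readings 4-9 remain uncovered.
- **The glucometer section points both ways.** Direction guides the choice of meter there ("Because GOx-based POC glucometers are known to underestimate BG while GDH-based POC glucometers do not"), but the same section also judges the meters by MARD.
- **The gain rests on assumed variances.** At +3.72% and 8% wander the signed tests have only 30% and 17% power.

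**Conclusion.** The point holds as a recommended change to the analysis. MARD answers whether average accuracy worsens, and should stay. It does not show whether the sensor shifts in one direction: under the normal model a +3.72% shift changes MARD by -0.54 to +1.42 points over baseline biases of -4% to +4%, against a 5-point target. At +10% with no average baseline bias, MARD power is about 32-47% against at least 97% for the signed same-day test. Baseline bias, wander, reading noise, lag and glucose slope are assumptions, not figures from the document. Whether a signed analysis could resolve a shift as small as 3.72% depends on wander and is not assured.

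The control-day question is an ambiguity to settle. It would be too strong to conclude that Aim 1 cannot be answered as planned, or that the session contrast should replace the same-day comparison.

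**What to change.** 1. Keep MARD on the HBO₂ day as the powered comparison; it detects added scatter, which a signed mean misses.
2. Add the mean signed relative difference (CGM minus laboratory, as a percentage of laboratory) with 95% CI, for readings 4-9 vs 1-3 and for 10-12 vs 1-3.
3. State whether Endpoint 1's phases cover the control day.
4. Beside the signed result, report a supporting phase-by-session (HBO₂ minus control) term for CGM error, from the mixed-model approach already planned for Endpoint 2. It is needed to interpret the signed result, given the lag effect above.

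This is a wording change only, since all 24 CGM and laboratory pairs per participant are already scheduled. The cost is precision in the supporting term. For MARD with a same-day SD of 8 and independent days, the contrast SD is 8√2 = 11.31. The half-width then grows from 3.4 to 4.8 points and power for 5 points falls from 83% to 55% (67% if the days correlate at 0.25, no loss at 0.5). Because control always comes first, the contrast does not remove day-order or sensor-age effects. No pass or fail margin is proposed.

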Payment		\$50		\$50	\$100		\$250
Event	Consent	Placement of CGM		Control Exposure - 3 hours	HBO ₂ Treatment - 3 hours		Return for CGM Removal
Event Log			Meals and Medication Times	Meals and Medication Times	Meals and Medication Times	Meals and Medication Times	
Home Testing			4 capillary measurements per day at home	4 capillary measurements per day at home	4 capillary measurements per day at home	4 capillary measurements per day at home	
Study Testing	UCG			Fingerstick measurement - POC x 12 Venous glucose - laboratory x 12	Fingerstick measurement - POC x 12 Venous glucose x 12		
				Glucagon x 3 Hba1c x 1	Glucagon x 3		
G6 CGM					Estimated Glucose Value		
G6 CG Logger					Interstitial Temperature		

Commercial CGMs have a 10-day lifespan and data loggers have a 14-day lifespan, but all study sessions should be completed within 10 days of insertion (Figure 2). The color coding represents whether or not participants and staff will have to come in over the weekend for a control or HBO₂ session (red), to insert CGMs or remove CGMs (yellow), or if they won't have to come in over the weekend at all (green).

Figure 2. Weekly schedule of events

Day	Description	Projected weekly schedule for 0730 am insertion						
		Monday	Tuesday	Wednesday	Thursday	Friday	Saturday	Sunday
1	Insertion of CGM	Monday	Tuesday	Wednesday	Thursday	Friday	Saturday	Sunday
2	36h Observation	Tuesday	Wednesday	Thursday	Friday	Saturday	Sunday	Monday
3	Control	Wednesday	Thursday	Friday	Saturday	Sunday	Monday	Tuesday
4	HBO ₂	Thursday	Friday	Saturday	Sunday	Monday	Tuesday	Wednesday
5	Observation	Friday	Saturday	Sunday	Monday	Tuesday	Wednesday	Thursday
6	Observation	Saturday	Sunday	Monday	Tuesday	Wednesday	Thursday	Friday
7	Observation	Sunday	Monday	Tuesday	Wednesday	Thursday	Friday	Saturday
8	Observation	Monday	Tuesday	Wednesday	Thursday	Friday	Saturday	Sunday
9	Observation	Tuesday	Wednesday	Thursday	Friday	Saturday	Sunday	Monday
10	Return CGM	Wednesday	Thursday	Friday	Saturday	Sunday	Monday	Tuesday

We will plan for recruitment of 24 individuals. Half will be patients living with type 1 diabetes and half will be patients living with type 2 diabetes.

Inclusion Criteria

- Diagnosis of type 1 or type 2 diabetes
- Willing to have 2 subcutaneous glucose monitors for 10 days
- Willing to be NPO after midnight on the day of the study session

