Confinement anxiety: Some individuals can experience confinement anxiety due to being in the chamber or wearing the oxygen hood or mask. To minimize this risk, we will screen potential participants for a history of confinement anxiety or other psychiatric disorders. Participants will always be accompanied in the chamber and will be reassured by highly trained staff. The chamber is very large (23 feet long and 7 feet in diameter) and is similar in size to a small aircraft cabin. Participants can terminate the exposure at any time and be removed from the chamber with a simple request. Participants can terminate the exposure and be removed from the chamber even there are non-study patients in the chamber at the same time.

Hypoglycemia: HBO₂ has been reported to decrease blood glucose in patients with DM. The hyperbaric department will follow their hypoglycemia protocol and provide supplemental carbohydrates if blood glucose is low either before or during HBO₂

Oxygen related seizure: Seizures occurring while someone is in a hyperbaric chamber are extremely uncommon and range from 0.02% - 0.04% in patients undergoing hyperbaric oxygen treatments at 2.0 to 2.5 ATA (Camporesi, E.M., 2014; Jokinen-Gordon, et al., 2017). The risk of seizures is increased with baseline neurologic disease and prior history of seizures. Screening will be done to determine if there is any increased risk by way of history taking and physical exam. A spontaneous oxygen seizure, should it occur, is self-limited and does not result in any long-term neurologic sequelae. The risk of seizure is only while someone is in the chamber and breathing oxygen. There is no risk after the hyperbaric exposure.

Oxygen related visual acuity changes: Hyperoxic myopia is a phenomenon that occurs after repeated hyperbaric exposures to 100% oxygen and is not a risk for study

December 4, 2019

participants as it does not typically present until individuals have had several weeks of HBO₂.

Pneumothorax: Pneumothorax, or collapsed lung, occurs in the extremely rare instances when individuals who have air-filled cysts in the lungs are exposed to rapidly changing pressures. Potential participants will be screened to make sure they have no history of lung disease. Pneumothorax is an extremely rare situation that requires medical and/or surgical treatment, such as inserting a tube through the skin into the chest to re-expand the collapsed lung.

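### Endpoint 1 compares MARD between phases without allowing for glucose level, so a change in blood glucose alone can move MARD when sensor error is partly constant in mg/dL

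*Combined protocol and SAP*

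**What the plan says.** Under Analysis, Endpoint 1, the plan states: "we will compare CGM values to laboratory results in the pre-HBO₂ NBAir (1-3), HBO₂ (4-9), and post-HBO₂ NBAir (10-12) phases". The only metric named is MARD: "We will compare the mean absolute relative difference (MARD), which is listed at 9.9% in the Dexcom G6 user guide". The sample size is set to "detect a difference of 5 percentage points in MARD (9.9% in room air up to 14.9% in HBO₂", and the result is that "we will require a minimum sample size of 18 patients". Recruitment is set higher: "We will plan for recruitment of 24 individuals".

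Endpoint 1 names no model, glucose covariate, glucose strata, error summary in mg/dL or control-day comparator. The one model in the Analysis section, a linear mixed model, belongs to Endpoint 2, where blood glucose is the outcome. The section on fingerstick point-of-care testing also uses MARD for the two glucometers, again without regard to glucose level.

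On glucose itself, Specific Aim 2 asks whether one HBO₂ treatment changes it and gives no direction. The Background discusses mechanisms for a drop with HBO₂ and, as an alternative theory, a downward trend that may already be present before treatment. The Hypoglycemia paragraph of the risk section says HBO₂ "has been reported to decrease blood glucose in patients with DM".

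**The concern.** The denominator of the Endpoint 1 metric is a quantity that the trial also studies as an outcome. If glucose differs between draws 1-3, 4-9 and 10-12, MARD can differ for two reasons: the sensor errs more under oxygen, or the same mg/dL error is divided by a smaller number. The planned comparison cannot tell these apart. The problem arises even when the sensor has no bias.

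It runs both ways. A fall in glucose can look like lost accuracy, and a rise can mask a real loss. Using the control day would remove only the drift common to both days. A change in glucose specific to HBO₂, which is the subject of Aim 2, would remain in the comparison.

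**Working it through.** **1. The plan's own figure.** Inputs from Endpoint 1: difference 5 points; SD 8 (the text says the listed MARD "has a standard deviation of 7.99 mg/dL"); alpha 0.05; "and a power of 0.80". Standardised difference = 5/8 = 0.625. A paired t-test (noncentral t), one-sided 0.05, gives n = 18 with power 0.816, which matches the plan. A two-sided test would need 23, and at n = 18 its power is 0.705. The plan does not state sidedness, and it prints the SD in mg/dL although it sets it against percentage points. Those are separate matters. Below, 8 is used as the SD of paired differences in percentage points.

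**2. How MARD depends on level.** Let f be the share of error constant in mg/dL, the rest being proportional to glucose. Calibrated to 9.9% at a starting level G0,

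MARD(G) = 9.9 × [(1 − f) + f × G0/G].

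The documents give neither G0 nor f. Assume G0 = 150 mg/dL and show f from 0 to 1.

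**3. A gradual fall, averaged over the HBO₂ phase.** Figure 4 of the blood sampling schedule puts draws 4-9 at T+25, 40, 60, 75, 95 and 110 minutes. Assume a linear fall of 50 mg/dL from T0 to draw 9: G(t) = 150 − 50t/110.

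| Draw | 4 | 5 | 6 | 7 | 8 | 9 | Mean |
|---|---|---|---|---|---|---|---|
| G (mg/dL) | 138.6 | 131.8 | 122.7 | 115.9 | 106.8 | 100.0 | 119.3 |
| 150/G | 1.082 | 1.138 | 1.222 | 1.294 | 1.404 | 1.500 | 1.273 |

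Phase MARD = 9.9 × [1 + f × 0.273]:

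| Additive share f | Phase MARD | Shift (points) | Chance of p < 0.05, n = 24, two-sided |
|---|---|---|---|
| 1 | 12.6% | 2.7 | 0.355 |
| 0.5 | 11.3% | 1.4 | 0.125 |
| 0.25 | 10.6% | 0.7 | 0.068 |
| 0 | 9.9% | 0 | 0.05 |

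The last column is the noncentral t probability with shift/8 as the standardised difference. Sensor behaviour is unchanged in every row.

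**4. What the whole 5 points would take.** With f = 1 and a constant level across the phase, 9.9 × 150/G = 14.9 gives G = 99.7, so glucose must average about 100 mg/dL over draws 4-9, a fall of 1 − 9.9/14.9 = 33.6%. On the linear path, glucose must reach about 75 mg/dL by draw 9 if error is wholly additive, and about 44 mg/dL if it is half additive.

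**5. A rise.** With f = 1, a phase at 180 mg/dL gives 9.9 × 150/180 = 8.25%, which would offset 1.65 points of true worsening.

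**6. Why mg/dL error alone is not the answer.** If error is purely proportional (f = 0), 9.9% is 14.85 mg/dL at 150 and 9.9 mg/dL at 100. A sensor that truly worsened to 14.85% would still show 14.85 mg/dL at 100, so the mg/dL summary would look unchanged. Each metric is blind under the opposite error structure. Separating the two requires error to be examined against glucose.

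**The case against.** **The full 5 points.** A reader might infer that a 50 mg/dL fall produces the entire design difference. That holds only if glucose is 50 mg/dL lower throughout draws 4-9 and error is wholly additive. For a fall that reaches 50 mg/dL at draw 9, averaging leaves 2.7 points at most. The half-additive path to 14.9% passes well below the 70 mg/dL level at which the modified glucose protocol provides carbohydrate, so such a path is implausible within this trial.

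**An expected fall.** A reader might also infer that the plan predicts falling glucose or that Aim 2 looks for it. Aim 2 has no direction, the pre-treatment trend is offered as a possibility, and the risk section reports past observation. The medication section holds or reduces many glucose-lowering doses before sessions, which bears on whether glucose falls at all. What remains is that the documents give reason to think glucose may differ between phases, and Endpoint 1 has no provision for it.

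**Sensor failure.** The plan does not say that a higher MARD would be read as sensor failure. It says MARD will be compared. Relative accuracy at the glucose levels actually present is a fair answer to Aim 1 as worded, which is a good reason to keep MARD as the headline. But the sizing contrast sets room air against HBO₂, and a difference framed that way invites attribution to oxygen.

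**Assumed inputs.** Every decisive input is assumed, and simulations with purely additive error restate that premise. This limits any claim about size. It does not remove the gap, since only an analysis of error against glucose can show which error structure applies.

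**Conclusion.** The point holds as a gap in interpretation. Endpoint 1 cannot separate an effect of oxygen on the sensor from an effect of glucose level on the metric, and nothing elsewhere in the document closes this. For the illustrative 50 mg/dL fall the shift is 0.7 to 2.7 points as the additive share goes from a quarter to the whole, and zero under purely proportional error. These figures rest on an assumed 150 mg/dL start, a linear fall and an assumed additive share, none of which the documents supply. They do not support a claim that the 5-point target would be reached by glucose change alone in ordinary conditions, or that the MARD comparison is invalid. The paired data needed are already planned, so this is a cheap improvement.

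**What to change.** Keep MARD by phase as the headline for Endpoint 1, and pre-specify two additions.

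1. Report the mean absolute CGM-laboratory difference in mg/dL by phase beside MARD.
2. Fit a supporting linear mixed model with participant as random effect, the absolute CGM-laboratory difference in mg/dL as outcome, and phase, session (HBO₂ or control) and laboratory glucose at that draw as covariates. Use the 12 paired values from each of the two days, and include a phase-by-session term so that draws 4-9 on the HBO₂ day have their own contrast. Report the HBO₂-versus-air difference at one common reference glucose named in advance. Using mg/dL as the outcome avoids having laboratory glucose both as the denominator of the outcome and as a covariate.

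Add one sentence on interpretation: a rise in MARD that is not also seen in the glucose-adjusted result should be read with caution as an oxygen effect on the sensor. An absolute rule would be too strong for 24 participants.

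The cost is one supporting analysis and a few sentences of text, with no new draws or visits. If HBO₂ does lower glucose, phase and glucose will be partly collinear and the adjusted intervals wider, and the report should say so. Specifying this now avoids choosing the error metric after the data are seen.
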